8.1.2 Pre-existing condition

[figure not shown]

Pre-existing medical conditions or symptoms reported prior to subject enrollment will not be recorded as an AE. In the event there is a worsening in the pre-existing medical condition or symptoms due to the device, implant procedure, or study related procedures, then an AE must be recorded.

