7.6 Secondary Endpoints and Clinical Outcomes

- Mitral regurgitation reduction at 30 days, 6 months, 1 year and annually thereafter over baseline
- All-cause mortality at 30 days, 6 months, 1 year, and annually thereafter
- Recurrent heart failure hospitalization at 30 days, 6 months, 1 year, and annually thereafter
- Re-intervention rates for mitral regurgitation at 30 days, 6 months, 1 year and annually thereafter
- Composite of major adverse events (MAE) defined as cardiovascular mortality, stroke, myocardial infarction, new need for renal replacement therapy, severe bleeding and re-intervention for study device related complications at 6 months, 1 year and annually thereafter
- Change in Left Ventricular End Diastolic Volume (LVEDV) at 6 months and 1 year and annually thereafter over baseline
- Change in Left Ventricular End Systolic Volume (LVESV) at 6 months and 1 year and annually thereafter over baseline
- Change in Pulmonary Artery Systolic Pressure at 6 months and 1 year and annually thereafter over baseline
- Change in 6MWT distance at 6 months and 1 year over baseline

- Change in Quality of Life (QoL) score, as measured by Kansas City Cardiomyopathy Questionnaire (KCCQ), and EQ5D at 30 days, 6 months and 1 year and annually thereafter over baseline
- Change in NYHA Functional Classification at 6 months and 1 year and annually thereafter over baseline
- Change in BNP/NT-pro-BNP level at 6 months and 1 year and annually thereafter over baseline
- Change in tricuspid regurgitation at 6 months and 1 year and annually thereafter over baseline
- Change in effective regurgitant orifice area (EROA) at 30 days, 6 months, 1 year and annually thereafter over baseline
- Change in mitral regurgitant volume at 30 days, 6 months and 1 year and yearly thereafter over baseline

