8 ADVERSE EVENTS, ADVERSE DEVICE EFFECTS AND DEVICE DEFICIENCIES

8.1 Reporting Procedure

Adverse events will be captured from the time of enrollment (after patient eligibility is confirmed, per section 7.8.3) until the study patient's participation has ended (i.e. completion of study or withdrawal of consent).

The Investigator will report all adverse events to the Sponsor as soon as possible, but no later than 10 working days after the Investigator first learns of the event (but no later than 3 calendar days after awareness for patients at EU sites)

Each adverse event must be reported on a separate AE CRF. In the event that the EDC system is not in service or is otherwise not accessible, the Sponsor must be notified by email

[REDACTED] The AE CRF should be completed as soon as possible thereafter.

At the time of initial notification, the following minimal information must be provided:

- Study site number
- Patient ID number
- Date of event
- Site's awareness date
- AE description
- Causal relationship to device and implant procedure, if known

The site will provide the Sponsor or designee copies of relevant supporting source documentation (e.g. admission H&P, implant procedure report, discharge summary, echocardiogram and laboratory results) for all adverse events requiring CEC adjudication (at a minimum, safety endpoints) and those events determined by the Sponsor to require additional investigation.

Study patients will be carefully monitored during the clinical study for any possible adverse event. All adverse events will be fully investigated by the Investigator. Appropriate treatment for the patient will be initiated while the study follow up continues. Adverse events must be followed

until resolution, the patient is lost to follow-up, the patient has withdrawn consent, or the adverse event is otherwise explained.

The Investigator will attempt to assess the involvement of the investigational device and / or study procedure in the adverse event. All observations and clinical findings, including the nature or the severity, will be documented on the appropriate case report form.

The Investigator will report all adverse events to their local Institutional Review Board/Ethical Committee and / or National Regulatory Agency in accordance with the applicable requirements.

8.1.1 Findings that do not require reporting to the sponsor:

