8.2.1 Adverse Event

An adverse event (AE) is defined in ISO 14155:2011 as any untoward medical occurrence, unintended disease or injury, or untoward clinical signs (including abnormal laboratory finding) in patients, users or other persons, whether or not related to the investigational medical device.

Note: anticipated adverse events are adverse events that have been identified as possible adverse events related to the investigational medical device or the study procedure. The anticipated events of this clinical study are summarized in Section 6.1.

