#### 7.7. Safety Variables

Number of unique subjects who experienced adverse events will be reported by AE category for each analysis cohort.

Events will be adjudicated by the CEC according to the CEC Charter. The CEC adjudicated adverse events will be summarized by KM estimate and/or binary proportions.

Number of unique subjects who experienced heart failure rehospitalization will be reported.

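### Protocol 8.1.2 can be read as requiring no AE for unrelated worsening of a pre-existing condition, contrary to the protocol's own AE definition and reporting rules

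*Protocol*

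**What the plan says.** Protocol 8.1.2 has two sentences. The first sets a default: "Pre-existing medical conditions or symptoms reported prior to subject enrollment will not be recorded as an AE". The second gives the sole exception, in which an AE is mandatory: "In the event there is a worsening in the pre-existing medical condition or symptoms due to the device, implant procedure, or study related procedures". Nothing in 8.1.2 deals with worsening from the natural course of disease or from an undetermined cause.

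Elsewhere the protocol does not make recording depend on cause. Section 8.2.1, and the AE entry in Section 17, define an AE as an untoward occurrence "in patients, users or other persons, whether or not related to the investigational medical device". Section 8.1 states the duty without qualification: "The Investigator will report all adverse events to the Sponsor as soon as possible". Section 8.2.7 has the investigator grade causality for each AE on five levels, the lowest being not related.

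The results that draw on these records are the early percentages and late linearized rates for all AEs (SAP 6.3), the secondary endpoint "Recurrent heart failure hospitalization at 30 days, 6 months, 1 year, and annually thereafter" (Protocol 7.6; Poisson regression in SAP 6.4), and the statement in SAP 7.7 that "Number of unique subjects who experienced heart failure rehospitalization will be reported".

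**The concern.** Section 8.1.2 puts the causality judgment before recording, whereas 8.2.7 puts it after. If the site decides first, an event called unrelated may never become an AE. The sponsor's own relatedness review (8.2.8) covers AEs, and the CEC and DSMB can act only on what reaches them, so none of these layers would be certain to see it.

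The population makes this more than a drafting detail. Inclusion criterion 3 requires NYHA class II, III or ambulatory IV heart failure, so every patient already has the condition whose worsening is both a safety signal and a secondary endpoint. The study has a single arm, so no comparison group would reveal under-recording.

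**Working it through.** The plan gives no figure on this point to reproduce. The check sets the provisions side by side and then traces the exposed results.

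**Step 1: what 8.1.2 requires.** Taken literally, the second sentence is a sufficient condition: related worsening must be recorded. It does not say that unrelated worsening must not be. But it is the only exception to a do-not-record rule, so a coordinator would naturally take it as complete.

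**Step 2: one hypothetical case under each provision.** A patient with cardiomyopathy has an unplanned admission of more than 24 hours at month 4 for decompensated heart failure treated with intravenous diuretics. The investigator attributes it to the cardiomyopathy.

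| Protocol provision | Treatment of the case |
|---|---|
| 8.1.2 | Exception not met; no AE form required |
| 8.2.1 and Section 17 (AE) | An AE, because the definition applies "whether or not related to the investigational medical device" |
| 8.1 | Reportable, as all AEs are |
| 8.2.7 | An AE graded for causality; attribution to an underlying illness is one listed ground for the not-related grade, and cases that cannot be assessed are classed as possible |
| Section 17 (SAE note) | Only a planned admission for a pre-existing condition, without serious deterioration, is excluded; this admission remains an SAE |
| Section 17 (rehospitalization) | A CHF hospitalization; primary heart failure counts whatever the cardiac cause |

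Section 8.1.2 stands alone against the rest.

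**Step 3: which conditions are exposed.** Heart failure is present in all patients (inclusion 3). Exclusion 24 removes only severe renal disease, so milder renal disease can be present at entry; the documents do not say how often.

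**Step 4: which results are exposed.**
- *All-AE summaries (SAP 6.3):* directly, since they count recorded AEs.
- *Heart-failure hospitalization (SAP 6.4 and 7.7):* conditionally. Protocol 7.8.7.9 requires CRF pages for unscheduled visits to cardiac departments, but does not say that these feed the endpoint or the CEC, and admissions to other departments fall outside it. Section 8.1 asks for source documents for AEs that need adjudication, with safety endpoints as the minimum; heart-failure hospitalization is not a component of the primary safety composite in 7.5.
- *30-day MAE (Protocol 7.5):* hardly. Cardiovascular death, stroke, myocardial infarction, severe bleeding and device-related re-intervention are ordinarily new events. Progression of existing renal disease to new renal replacement therapy is the component that could be read as worsening of a baseline condition.

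**Step 5: direction and size.** Recorded events = true events − unrelated worsenings left unrecorded. The subtracted term is zero or positive, so any bias is downward. A patient whose event is not recorded looks event-free, not missing, so the numerator falls and the denominator stays. With the planned 60 patients, each patient missed lowers a patient-level percentage by 1/60 = 1.7 percentage points. The number missed depends on the true event rate, the share judged unrelated and the share recovered by another route. The documents give none of these, so the calculation stops there.

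**The case against.** The strongest reply is that 8.1.2 never says only. Its first sentence can be taken to cover baseline status alone, leaving the general duty in 8.1 and 8.2.1 to govern later worsening. The SAE note in Section 17 implies that an unplanned admission for a pre-existing condition is an SAE. The rehospitalization definition covers unplanned admissions of any cause and would make little sense if only device-related ones were collected. There are other routes too: the unscheduled-visit CRF pages, a safety evaluation at every visit, and separate procedures for deaths. The CRFs and the CEC charter are not part of the documents and may settle the matter.

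Much of this stands. The word only is an inference, and these provisions may recover many heart-failure events. But none of them says that it overrides 8.1.2 or that unrelated worsening needs an AE form. They show what the protocol probably intends, and they are also what 8.1.2 contradicts.

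A reader might go further and infer that the 30-day MAE rate is materially understated, or that heart-failure hospitalizations are understated by some large stated percentage. The documents support neither. Most MAE components are new events, and a percentage would only restate an assumed related share while also assuming that no other route captures anything.

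**Conclusion.** The inconsistency is real and should be corrected, in this limited form: 8.1.2, as a site would naturally read it, does not require an AE for unrelated worsening of baseline disease, while 8.1, 8.2.1, 8.2.7 and Section 17 do. The text shows that events can go unrecorded, not that any were.

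The conclusion rests on two assumptions: that sites treat the stated exception as exhaustive and, for heart-failure hospitalization only, that no CRF or charter route outside these documents captures the admissions independently of AE reporting. If the second fails, the exposure shrinks to the all-AE summaries. Sample size and the planned analysis methods are not affected.

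**What to change.** Replace the second sentence of 8.1.2 with wording such as: *Any clinically significant worsening, after enrollment, of a condition present at baseline is recorded as an AE whatever its cause; its relationship to the device and procedure is then graded under 8.2.7.*

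Add to 8.1 that unplanned hospitalizations and potential endpoint events are submitted for CEC adjudication regardless of the investigator's view of relatedness. If a separate CRF already collects hospitalizations for SAP 6.4 and 7.7, name it in the protocol and the SAP.

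The cost is a short amendment, notification of sites and some additional AE forms.

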8.2 Adverse Event Definitions and Classification

Figure 10: Adverse Event Classification

8.2.1 Adverse Event

An adverse event (AE) is defined in ISO 14155:2011 as any untoward medical occurrence, unintended disease or injury, or untoward clinical signs (including abnormal laboratory finding) in patients, users or other persons, whether or not related to the investigational medical device.

Note: anticipated adverse events are adverse events that have been identified as possible adverse events related to the investigational medical device or the study procedure. The anticipated events of this clinical study are summarized in Section 6.1.

8.2.2 Adverse Device Effect

An adverse device effect (ADE) is defined in ISO 14155:2011 as any adverse event related to the use of an investigational medical device. This definition includes:

- Adverse event resulting from insufficient or inadequate IFU, deployment, implantation, installation, or operation, or any malfunction of the investigational medical device.
- Any event resulting from use error or from intentional misuse of the investigational medical device.

8.2.3 Serious Adverse Event

A serious adverse event (SAE) is defined in ISO 14155:2011 as an adverse event that:

- led to death
- led to serious deterioration in the health of the patient that either resulted in:
 - a life-threatening illness or injury, or
 - a permanent impairment of a body structure or a body function, or
 - in-patient or prolonged hospitalization, or
 - Medical or surgical intervention to prevent life threatening illness or injury or permanent impairment to a body structure or a body function.
- Led to fetal distress, fetal death or a congenital abnormality or birth defect (not anticipated in this study as pregnant women are excluded from the study).

8.2.4 Serious Adverse Device Effect

A serious adverse device effect (SADE) is defined in ISO 14155:2011 as an adverse device effect that resulted in any of the consequences characteristics of a serious adverse event or that might have led to any of these consequences if suitable action had not been taken or intervention had not been made or if circumstances had been less opportune.

8.2.5 Unanticipated Adverse Device Effect

Unanticipated adverse device effect (UADE) means any serious adverse effect on health or safety or any life-threatening problem or death caused by, or associated with, a device, if that effect, problem, or death was not previously identified in nature, severity, or degree of incidence in the investigational plan or application (including a supplementary plan or application), or any other unanticipated serious problem associated with a device that relates to the rights, safety, or welfare of subjects. (21 CFR part 812.3 (s)).

8.2.6 Unanticipated Serious Adverse Device Effect

Unanticipated adverse device effect (USADE) is defined in ISO 14155:2011 as any serious adverse device effect which by its nature, incidence, severity or outcome has not been identified in the risk analysis section of the study protocol.

8.2.7 Adverse Event Causality Assessment

For each AE, the Investigator will determine whether the event is related to the device and/or the implant procedure, and whether the event meets the definition of a SAE as outlined in section 8.2.3

For the purpose of this study, each AE will be classified according to five different levels of causality per MEDEV 2.7/3 rev. 3 May 2015 as follows:

Not related: relationship to the device or procedures can be excluded when:

- the event is not a known side effect of the product category the device belongs to or of similar devices and procedures;
- the event has no temporal relationship with the use of the investigational device or the procedures;
- the serious event does not follow a known response pattern to the medical device (if the response pattern is previously known) and is biologically implausible;
- the discontinuation of medical device application or the reduction of the level of activation/exposure - when clinically feasible - and reintroduction of its use (or increase of the level of activation/exposure), do not impact on the serious event;
- the event involves a body-site or an organ not expected to be affected by the device or procedure;
- the serious event can be attributed to another cause (e.g. an underlying or concurrent illness/ clinical condition, an effect of another device, drug, treatment or other risk factors);
- the event does not depend on a false result given by the investigational device used for diagnosis, when applicable;
- harms to the subject are not clearly due to use error;
- In order to establish the non-relatedness, not all the criteria listed above might be met at the same time, depending on the type of device/procedures and the serious event.

Unlikely: the relationship with the use of the device seems not relevant and/or the event can be reasonably explained by another cause, but additional information may be obtained.

Possible: the relationship with the use of the investigational device is weak but cannot be ruled out completely. Alternative causes are also possible (e.g. an underlying or concurrent illness/ clinical condition or/and an effect of another device, drug or treatment). Cases where relatedness cannot be assessed or no information has been obtained should also be classified as possible.

Probable: the relationship with the use of the investigational device seems relevant and/or the event cannot reasonably be explained by another cause, but additional information may be obtained.

Related: the serious event is associated with the investigational device or with procedures beyond reasonable doubt when:

- the event is a known side effect of the product category the device belongs to or of similar devices and procedures;
- the event has a temporal relationship with investigational device use/application or procedures;
- the event involves a body-site or organ that
 - the investigational device or procedures are applied to;
 - the investigational device or procedures have an effect on;
- the serious event follows a known response pattern to the medical device (if the response pattern is previously known);
- the discontinuation of medical device application (or reduction of the level of activation/exposure) and reintroduction of its use (or increase of the level of activation/exposure), impact on the serious event (when clinically feasible);
- other possible causes (e.g. an underlying or concurrent illness/ clinical condition or/and an effect of another device, drug or treatment) have been adequately ruled out;
- harm to the subject is due to error in use;
- the event depends on a false result given by the investigational device used for diagnosis, when applicable;
- In order to establish the relatedness, not all the criteria listed above might be met at the same time, depending on the type of device/procedures and the serious event.

The sponsor and the investigators will distinguish between the serious adverse events related to the investigational device and those related to the procedures (any procedure specific to the clinical investigation). An adverse event can be related both to procedures and the investigational device. Complications of procedures are considered not related if the said procedures would have been applied to the patients also in the absence of investigational device use/application.

In some particular cases the event may not be able to be not adequately assessed because information is insufficient or contradictory and/or the data cannot be verified or supplemented. The sponsor and the Investigators will make the maximum effort to define and categorize the event and avoid these situations.

8.2.8 Sponsor Assessment of Adverse Events

All AEs will be reviewed by the Sponsor's Clinical Safety department. Each AE will be assessed as to its relationship to the study device and/or implant procedure, whether it was anticipated or not anticipated, (based on the list of potential risks provided in section 6), and whether it qualifies as an SAE.

8.2.9 Device Deficiency and Malfunction

Device deficiency is defined in ISO 14155:2011 as an inadequacy of a medical device with respects to its identity, quality, durability, reliability, safety or performance. Device deficiencies include malfunctions, use errors and inadequate labeling.

Device malfunction is defined in ISO 14155:2011 as a failure of an investigational medical device to perform in accordance with its intended purpose when used in accordance with the IFU. All reported device observations, malfunctions or deficiencies for the Edwards PASCAL System are required to be documented on the appropriate eCRF. In the event of a suspected observation or device problem, the device shall be returned to the Sponsor to the extent possible for analysis. Instructions for returning the investigational device will be provided by the Sponsor.

8.3 Deaths and Explants

8.3.1 Patient Deaths

In the event of patient death, every effort should be made to obtain a copy of the autopsy report and/or death summary. Information on the cause of death and its relationship to the investigational device or study procedure will be determined by the Investigator. Copies of an autopsy report, if available, and/or a death summary are to be forwarded to the Study Sponsor. If a device is explanted during autopsy, the device should be returned to the Study Sponsor for analysis. Return kits for devices will be provided upon request by the clinical monitor.

8.3.2 Device Explants

In the event the study device(s) is explanted, in the intra-operative or early post-operative period a copy of the explant procedure report must be provided to the Study Sponsor. Information on the cause of explant and its relationship to the study devices will be determined by the Investigator. Explanted study devices during this period should be returned to Study Sponsor for analysis.

In the event the study device is explanted, in the late post-operative period, every effort should be made to obtain a copy of the explant procedure report, as applicable. Information on the cause of explant and its relationship to the study device will be determined by the Investigator. Copies of an explant report, if available, are to be sent to the Study Sponsor. Explanted study devices during this period should be returned to Study Sponsor for analysis.

